4.2 Compliance to confirmatory endoscopies

Compliance to confirmatory endoscopies will be measured out of all patients receiving a low or high-confidence positive Cytosponge™ test result. We will report on number of attenders and types of diagnoses.

4.3 Compliance to research endoscopies (after end of follow-up)

Compliance to research endoscopies will be measured out of all patients receiving an invite to a research endoscopy. We will report on number of responders, interested/not interested, attenders and types of diagnoses both overall and by study arm.

Note: only participants in the usual care arm and patients receiving a negative Cytosponge™ test result were invited to a research endoscopy. A limited number of 'non-responders', i.e. patients who did not take up their Cytosponge™ invitation, were also invited to research endoscopies at the beginning of the rollout of this part of the trial; their invites were suspended shortly after. Despite the small figures, we will report on number of non-responders invited and attending a research endoscopy in the final statistical report.

5. Demographics and baseline characteristics

The following data will be available at baseline for each GP practice:

Usual care, intervention and PLR practices will send the study team the following baseline data in *aggregated* form (Excel spreadsheet see below):

- Number of participants enrolled by sex and age group
- Drugs administered and dosage

For PLR practices, the trial arm is not included in the aggregated baseline data.

Sex	Age bracket (yrs)					Total
	50-59	60-69	70-79	80-89	90-99	
Female						
Male						
Total						

Demographics and baseline characteristics will be presented by summary statistics. No statistical tests will be performed to compare these between study arms.

Number of sites, number of participants per study arm and average practice size will also be presented.

Patients who take up the Cytosponge™ invitation will have to complete the following CRFs, with the following information available to the Trial Statistician:

- Personal details CRF: sex, year of birth, ethnicity (sensitive data, available to the Statistician via the Trial Senior Research Application Programmer only)
- Allergies CRF
- Baseline Clinical CRF: height, weight, waist/hip circumference, medication for reflux symptoms and dose, gastro-oesophageal reflux disease impact scale questionnaire, heartburn start, H. Pylori, comorbidities
- Baseline Questionnaire CRF: education, smoking history, alcohol intake, risk perception, STAI 6 questionnaire, family history

A number of patients selected at random, both in the usual care and the intervention arm, will have their baseline data and any data regarding a potential upper GI diagnosis and treatment reviewed at the end of their follow-up period. When possible,

sites will review the records of all their patients and fill in a case-note review CRF for each one of them.

A copy of all CRFs is available here:

[G:\EMS\CPTU\BEST3\Section 10 CASE REPORT FORM \(CRF\)\10.1 Current version\BEST3 eCRFs](G:\EMS\CPTU\BEST3\Section 10 CASE REPORT FORM (CRF)\10.1 Current version\BEST3 eCRFs)

5.1 Characteristics collected during the study

Participants taking up the Cytosponge™ invitation will also see the following information gathered on them:

- 7-14 day follow-up questionnaire CRF: questions on different elements of the test experience, perceived risk of oesophageal cancer, STAI 6

5.2 End-of-study data

A number of patients selected at random by the Trial Statistician, both in the usual care and the intervention arm, will have their demographics data collected at the end of their follow-up period. These will be the same patients randomly selected to have their baseline data reviewed and a case-note review CRF will be filled in for each one of them.

The primary endpoint data on BE diagnosis will be collected via local coded search + manual case-note review + NHS number linkage as explained in Section 2.3.

5.3 Prior medications and treatments

Acid suppression medication data at baseline is available in aggregated form for all practices. Only medication dose and drug name (not length of treatment) will be available for all individuals.

A number of patients selected at random, both in the usual care and the intervention arm, will have their medication data at baseline reviewed and their medication data at end of study collected at the end of their follow-up period. A case-note review CRF will be filled in for each one of them. For these patients, length of treatment will be available in three monthly categories up to one year and more than one year.

Aggregated data on medication will be compared to medication data gathered during case-note reviews in those practices performing a review of all of their patients.

6. Interim analysis and timing for analysis

6.1 Interim analysis

A Milestone 1 review was planned in January 2018 after six months of opening the first GP site to evaluate the proportion of eligible individuals per surgery (% of population covered), the proportion of participating individuals (% of eligible population), and the Cytosponge™ uptake. This eventually led to a review of the sample size and of the study design (from CLR to CLR and PLR). For more details on this, see Section 2.5.1.

Closed endpoint data on participants who took up the Cytosponge™ invitation were presented at the closed sessions of the DMC meetings of March 2018, October 2018 and October 2019. Reports for the closed session meetings are available here:

[G:\EMS\CPTU\BEST3\Section 17 TRIAL COMMITTEES\Data Monitoring Committee \(DMC\)\Meetings \(agenda and minutes\)\Reports for closed session](G:\EMS\CPTU\BEST3\Section 17 TRIAL COMMITTEES\Data Monitoring Committee (DMC)\Meetings (agenda and minutes)\Reports for closed session)

6.2 Time-points for analysis

Only a statistical analysis at the end of the trial is planned.

The last patients were randomised into the trial on 05/04/2019. The coding for the statistical analysis will start in October 2019. The final data lock is expected to happen on 31 January 2020.

7. Efficacy analysis

The statistical analysis will be run using Stata and R. The trial statistician will write the code, which will then be checked by another statistician. The primary analysis of the primary endpoint will be undertaken independently by a second statistician. If the two analyses do not produce identical results, the two statisticians will review their analyses together to reach consensus.

7.1 Method for analysis of endpoints

7.1.1 Analysis of primary endpoint

The power under various assumptions regarding sensitivity, BE prevalence and intra-class correlation will be calculated based on the actual numbers recruited, the uptake observed and the actual duration of follow-up.

Null Hypothesis: The BE detection rate at 12 months (excluding any found on random exit endoscopies) is the same in the intervention arm and the control (usual care) arm.

Alternative hypothesis: The BE detection rate at 12 months is greater in the intervention arm than in the control (usual care) arm.

The CLR and PLR group will be first analysed separately; if the results from the two parts of the study favour the test, a combined analysis will be performed.

Primary endpoint data will be collected according to the methods explained in Section 2.3. This aims at guaranteeing an equal approach to data collection in the two study arms, but implies that, for the primary endpoint analysis, we will only consider BEs that were ascertained systematically through one of the three methods.

Sites have variable follow-ups. The number of person-years of follow-up will be calculated by taking as the end date the date of the local coded search in a practice and as start date the date the first letter of introduction to the study was sent plus 15 days. Follow-up will be considered until whichever is first: diagnosis of BE, the date of the systematic search for BE, the day before a research endoscopy. BE found on research endoscopy will not be counted towards the primary endpoint.

Rates will be calculated out of 1000 person-years. A single rate will be calculated during follow-up in the control arm. Two rates will be calculated in the intervention arm: the rate within four months of randomisation and the rate beyond four months from randomisation. In order to estimate the average rate within 12 months of randomisation in the intervention arm, a weighted average of these two rates will be taken with weights 2:1.

The methods mentioned in the sections below are taken from:

Hayes RJ and Moulton LH. (2009). *Cluster randomised trials*. ed. Boca Raton, FL: Chapman & Hall/CRC, pp. 178-9.

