2.5.4 Variable follow-up periods

Because of delays in the implementation of the change of study design (from CLR to CLR with additional PLR group), it was decided that participants/practices could have

a follow-up longer than 12 months to compensate for participants/practices who will have a follow-up shorter than 12 months due to time constraints.

Different practices will have different follow-ups as long as the **weighted average follow-up** for the study will be greater than 12 months, as shown by the following formula:

$$\text{avg}_{\text{FU}} = \frac{\sum_{i=1}^P F_i M_i + \sum_{j=1}^Q F_j N_j}{\sum_{i=1}^P M_i + \sum_{j=1}^Q N_j} \geq 12$$

where F_i, F_j are the different lengths of follow-up (in months) for each different group, M_i are the numbers of patients with different follow-ups in the CLR group in 'equivalent size' terms, N_j are the numbers of patients with different follow-ups in the PLR group, $\sum_{i=1}^P M_i$ is the total size (in 'equivalent' terms) of the CLR group, and $\sum_{j=1}^Q N_j$ is the total size of the PLR group.

According to our current projections, all practices will have between 8 and 18 months of follow-up. The end date of follow-up will be when a site performs their local coded search; it will therefore be taken from the Coded Search case report form (CRF).

Note: in case a weighted average follow-up of 12 months or more could not be guaranteed, the power of the study would be less than 90%. The following table illustrates the potential loss in power with shorter follow-up:

Total average follow-up (months)	Factor by which to inflate sample size
9	1.24
9.5	1.18
10	1.13
10.5	1.09
11	1.06
11.5	1.03

A detailed explanation on how to calculate the factors by which to inflate the sample size is available here:

[G:\EMS\CPTU\BEST3\Section 26 STATISTICS\26.3 Power calculations\Sample size \(following Amendment 6\)\BEST3_Sample size.pdf](G:\EMS\CPTU\BEST3\Section 26 STATISTICS\26.3 Power calculations\Sample size (following Amendment 6)\BEST3_Sample size.pdf)

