3.3 Subgroup definitions

Primary endpoint analysis will be carried out separately for the CLR and PLR groups as asked by the Medicines and Healthcare products Regulatory Agency (MHRA) in a communication on 31 May 2018. If the results from both subgroups favour the study intervention, i.e. the proportion of participants with diagnosed BE is greater (regardless of the level of significance) in the invitation to the Cytosponge™ arm than in the usual-care arm, then a combined analysis shall be performed.

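### Usual care gets one crude rate and the intervention arm a two-period weighted rate, so the 12-month rate ratio rests on an unstated constant usual-care rate

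*SAP*

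**What the plan says.** The null hypothesis in SAP section 7.1.1 is that the 12-month detection rate "is the same in the intervention arm and the control (usual care) arm". The same section then summarises the arms differently:

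- Usual care: "A single rate will be calculated during follow-up in the control arm".
- Intervention: "Two rates will be calculated in the intervention arm", namely "the rate within four months of randomisation and the rate beyond four months from randomisation". To represent 12 months, "a weighted average of these two rates will be taken with weights 2:1".

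The mixed Poisson model for the cluster-randomised (CLR) group in section 7.1.1.1 has two records per patient, split at four months. Its fixed effects are treatment and stratum, with a treatment effect for each period. The overall effect is a weighted mean of those two, obtained with `nlcom`. No period main effect is mentioned, and neither the weights nor the scale of the mean are given.

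Section 2.5.4 projects that "all practices will have between 8 and 18 months of follow-up". It accepts this variation with a study-wide condition: "Different practices will have different follow-ups as long as the" weighted average is at least 12 months. Section 3.3 adds: "Primary endpoint analysis will be carried out separately for the CLR and PLR groups". A combined analysis follows only if both groups favour the intervention.

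**The concern.** A crude rate over follow-up of mean length F weights the first four months by 4/F and the rest by (F − 4)/F. The intervention summary uses fixed weights whatever F is. If detection in usual care is not constant over time, two arms with identical rates need not give a ratio of 1.

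The SAP gives no reason to take the usual-care rate as constant. Everyone receives an introductory letter (section 3.4), and follow-up starts 15 days after it is sent. Follow-up ends at the practice's coded search. A short-lived rise in consultations after the letter, or late coding of recent diagnoses, is conceivable. The SAP has no data on either.

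The 12-month floor applies to the whole study, in equivalent-size terms. It does not apply to the CLR group or the patient-level randomised (PLR) group alone, although these are analysed first and their directions decide whether they are combined. At stake are the primary estimate, its interval and the comparability of the two groups.

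**Working it through.** **The plan's own figures (section 2.5.2).** Intervention: 0.27 × [0.04 × 0.85 + 0.15 × 0.1 × 0.06] + 0.73 × 0.1 × 0.06 = 1.3803%. Usual care: 0.1 × 0.06 = 0.6%. The planned ratio is 1.3803/0.6 = 2.30. The unrounded value at 90% power, two-sided 5%, reproduces the stated total of 6764.

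**Inputs.** Split at 4 months and follow-up of 8–18 months (SAP). Assumption: the early/later background rate ratio r is 2 or 0.5, equal in both arms, with no effect of the intervention. Later rate set to 1.

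**Formulas.**
- Crude usual-care rate: (4r + F − 4)/F
- Intervention, time-proportional weights (4/12, 8/12): (r + 2)/3
- Intervention, weights as printed (2:1, early then later): (2r + 1)/3

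Example, r = 2 and F = 10: crude = (8 + 6)/10 = 1.40; 1:2 gives 1.333/1.40 = 0.95; 2:1 gives 1.667/1.40 = 1.19.

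**Rate ratio when the arms are identical**

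| Mean follow-up (months) | r = 2, 1:2 | r = 2, 2:1 | r = 0.5, 1:2 | r = 0.5, 2:1 |
|---|---|---|---|---|
| 8 | 0.89 | 1.11 | 1.11 | 0.89 |
| 10 | 0.95 | 1.19 | 1.04 | 0.83 |
| 12 | 1.00 | 1.25 | 1.00 | 0.80 |
| 15 | 1.05 | 1.32 | 0.96 | 0.77 |
| 18 | 1.09 | 1.36 | 0.94 | 0.75 |

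With r = 1 every entry is 1.00. If both arms are split and weighted alike, every entry is 1.00 for any r and F.

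**Which weights represent 12 months.** Assume all Cytosponge-detected cases (0.27 × 0.04 × 0.85 = 0.918%) fall in the first four months and the other 0.4623% are spread evenly. The early rate is then 3 × 9.18 + 4.623 = 32.2 per 1000 person-years and the later rate 4.6. Weights 1:2 return 13.8, the planned figure (ratio 2.30). Weights 2:1 return 23.0 (ratio 3.83).

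**The regression without a period term.** Both treatment effects then share one usual-care rate. With r = 2, F = 12 and no effect, that rate is 1.333 and the period ratios are 2/1.333 = 1.50 and 1/1.333 = 0.75. Their 1:2 mean is 1.00 on the ratio scale, but (1.50 × 0.75²)^(1/3) = 0.94 on the log scale.

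**Why a period term alone is not enough.** Let a1, a2 be the early and later intervention rates and c1, c2 those in usual care. The 12-month ratio is (a1 + 2a2)/(c1 + 2c2). The weighted mean of a1/c1 and a2/c2 equals this only in special cases, such as c1 = c2 with averaging on the ratio scale. At the planning rates above and a constant 6.0 in usual care, the period ratios are 5.36 and 0.77. Their 1:2 mean on the log scale is 1.47, against 2.30.

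**Variance cost of standardising usual care (constant rate).** F × [(1/9)/4 + (4/9)/(F − 4)] = 1.11, 1.02, 1.00, 1.02 and 1.07 at F = 8, 10, 12, 15 and 18.

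**The case against.** The best defence is parsimony. Usual care has no timed intervention and few events, so a single rate is reasonable. With 1:2 weights the harm is slight. Take 5390 PLR patients (2695 per arm), 0.6% a year, 10 months and r = 2. That gives 2695 × 0.006 × 10/12 = 13.5 events per arm and a log-ratio standard error of √(2/13.5) = 0.385. The bias of ln 0.952 = −0.049 is about 0.13 standard errors, and two-sided type I error moves from 5.0% to about 5.2%. This stands as a limit on size. It does not justify the asymmetry, because treating both arms alike costs almost nothing.

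A reader might infer three stronger points that the SAP does not support:

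- *The arms are observed over different time windows.* They are not. Follow-up ends by the same rule in both arms, PLR arms share practices, and the intervention arm's second period also runs to 18 months. Only the weighting of the periods differs.
- *The primary regression is shown to ignore time in usual care.* The SAP leaves this open. Section 7.1.1.1 splits every patient's follow-up, its PLR text does not limit the two-period rate to one arm, and section 7.2 says the analysis is by period.
- *CLR is biased one way and PLR the other.* The SAP gives no mean follow-up by group. Short PLR follow-up is plausible, since later practices used PLR and under 10 months separate the last randomisation (05/04/2019) from the expected data lock (31/01/2020). The 10- and 15-month figures remain illustrations.

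**Conclusion.** The concern holds in a limited form. Section 7.1.1 weights the two periods differently in the two arms, and section 7.1.1.1 does not say whether usual care has its own period effect. The 12-month ratio is therefore unbiased under no effect only if the usual-care rate is constant or, with 1:2 weights and averaging on the rate scale, if the analysed group's mean follow-up is 12 months.

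For an assumed twofold change in the background rate, the departure with 1:2 weights is nil at 12 months, about 5% at 10 or 15, and 9–11% at the extremes. That is small against the planned ratio of 2.3 and unlikely to reverse the direction rule for combining the groups. With the weights read as printed it is 25% at 12 months, so near the planned follow-up the printed 2:1 weighting matters more than the crude control rate. All sizes depend on the assumed r, for which the SAP gives no information. The text should be corrected before analysis; a materially wrong test has not been shown.

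**What to change.** 1. In section 7.1.1, estimate two rates in both arms, split at four months. Standardise each arm to 12 months with weights 4/12 for the early rate and 8/12 for the later rate.
2. In the CLR, PLR and combined Poisson models, include a period main effect alongside the period-specific treatment effects.
3. Change the `nlcom` step to the ratio of the arms' standardised rates, in place of the weighted mean of the two period-specific treatment effects.
4. Bring the PLR text and section 7.2 into line with this.

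The cost is SAP wording, one model term and a changed `nlcom` expression. The planned two records per patient already give the data structure needed. Control-arm variance rises by about 0% at a mean follow-up of 12 months, 2% at 10 or 15, 7% at 18 and 11% at 8.

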7.1.1.1 Unadjusted analysis

CLR group

The CLR group is stratified by cluster size, i.e. number of participants per practice, as per the categories defined in the Milestone 1 review of the sample size (see Section 2.5.2): 50-65, 66-90, 91-125, 126-175, 176-225.

As a primary analysis, we will run a regression analysis based on individual-level data, followed by a secondary analysis based on cluster-level summaries to ensure that the conclusions are robust.

We will report on number of clusters and patients by stratum and study arm, and on the weighted average follow-up for the CLR group as shown in Section 2.5.4.

Individual-level data

We will first report on cumulative BE detection rate at one year (/ 1000 person-years) by stratum and study arm, and overall, using individual-level data. The one-year rate in the intervention arm will be estimated assuming a constant rate in the first four months and a (possibly different) constant rate thereafter (up to 18 months).

Primary endpoint data will be analysed by a mixed-effects Poisson regression for BE with fixed effects for the treatment and random effects to account for between-cluster variation (i.e. a random effect for the level of BE in each GP practice), with the number of person-years of follow-up as the offset. Additional fixed effect parameters will be included to account for strata (size of clusters in each stratum: 50-65, 66-90, 91-125, 126-175, 176-225).

The resulting 12-month rate ratio will be reported with 95% confidence interval and will be formally tested to see if it is significantly greater than 1.0 (with a two-sided alpha of 0.05).

To fit the Poisson regression random effects model to data, we will model the random effects using a log-gamma distribution.

In Stata, the `mepoisson` command performs a mixed-effects Poisson regression. See Section 11.2.1.1 of Hayes and Moulton for an explanation on the method. There will be two observations (and two durations of follow-up) for each patient: one for the first four months and a second thereafter. There will be a separate treatment effect for each period. The overall treatment effect will be calculated as the weighted mean of the two treatment effects using the Stata command `nlcom`.

Cluster-level data

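### The 12-month intervention rate averages a 4-month rate and an 8-month rate with weights 2:1; the weights must be 1:2, and the scale of the averaging must be stated

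*SAP*

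**What the plan says.** Section 7.1.1 defines one rate for the control arm and two for the intervention arm: "the rate within four months of randomisation and the rate beyond four months from randomisation". On units it says "Rates will be calculated out of 1000 person-years". The two are combined to "estimate the average rate within 12 months of randomisation in the intervention arm", and the rule is that "in the intervention arm, a weighted average of these two rates will be taken with weights 2:1".

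Section 7.1.1.1 (CLR group, individual-level data) takes each intervention-arm rate as constant within its period, with the change at four months and follow-up to at most 18 months. For the mixed-effects Poisson model it fits a separate treatment effect in each period and adds: "The overall treatment effect will be calculated as the weighted mean of the two treatment effects using the Stata command" nlcom. It gives neither weights nor scale for that step. The cluster-level analysis and the PLR analysis use the same split at four months for the 12-month rate, and the combined analysis repeats the CLR methods. The only weights anywhere in the SAP are those in section 7.1.1.

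**The concern.** The first rate named covers 4 of the 12 months and the second covers 8. A 12-month average of two annualised, piecewise-constant rates is weighted by time, which is 1:2 in the order named. The stated 2:1 gives the shorter period double weight.

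This matters because the estimate is the trial's main result, and a separate early rate is needed precisely because detection may be front-loaded after the offer of the test. With reversed weights the quantity is no longer the 12-month detection rate that the null hypothesis in section 7.1.1 and the sample size in section 2.5.2 refer to. Section 7 has a second statistician run the primary analysis independently, but that would not catch the error if both follow the same sentence.

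**Working it through.** **Inputs.** From section 2.5.2: BE prevalence 4%, Cytosponge sensitivity 85%, endoscopy in usual care 10%, BE among those referred 6%, uptake 27%. From section 7.1.1: the two periods and the weights. Not in the SAP, so an assumption: *f*, the share of Cytosponge-triggered diagnoses made within four months, taken from 1/3 (no front-loading) to 1.

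**Step 1, the plan's own figures.**
- Cytosponge-triggered: 0.27 × 0.04 × 0.85 = 0.918%.
- Other diagnoses in the intervention arm: 0.27 × 0.15 × 0.006 + 0.73 × 0.006 = 0.4623%.
- Sum: 1.3803%, the SAP's 1.38%.
- Usual care: 0.1 × 0.06 = 0.6%.
- Ratio: 1.3803 / 0.6 = 2.30.
- The standard two-proportion formula (two-sided 5%, 90% power) then gives 3382 per arm, 6764 in all, as in the SAP.

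**Step 2, period rates per person-year.**
- Early: r1 = (f × 0.918% + 0.4623% × 4/12) / (4/12)
- Later: r2 = ((1 − f) × 0.918% + 0.4623% × 8/12) / (8/12)
- Time-weighted average: (r1 + 2·r2)/3
- Average as written: (2·r1 + r2)/3

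**Step 3, results per 1000 person-years, control 6.0.**

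| f | r1 | r2 | 1:2 average | Ratio | 2:1 average | Ratio | Excess |
|---|---|---|---|---|---|---|---|
| 1/3 | 13.8 | 13.8 | 13.8 | 2.30 | 13.8 | 2.30 | 0% |
| 1/2 | 18.4 | 11.5 | 13.8 | 2.30 | 16.1 | 2.68 | 17% |
| 3/4 | 25.3 | 8.1 | 13.8 | 2.30 | 19.5 | 3.26 | 42% |
| 0.9 | 29.4 | 6.0 | 13.8 | 2.30 | 21.6 | 3.60 | 57% |
| 1 | 32.2 | 4.6 | 13.8 | 2.30 | 23.0 | 3.83 | 67% |

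Weights 1:2 return the design value for every f. Weights 2:1 do so only when the two rates are equal, in which case no split is needed. At the 24% uptake of section 2.5.3 and f = 1, the ratios are 2.16 (1:2) and 3.52 (2:1), an excess of 63%.

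**Step 4, diagnoses only brought forward.** Let both arms reach 0.6% by 12 months, with half of all intervention-arm cases in the first four months. Then r1 = 3.0/(4/12) = 9.0 and r2 = 3.0/(8/12) = 4.5 per 1000. Weights 1:2 give (9.0 + 9.0)/3 = 6.0, ratio 1.00. Weights 2:1 give (18.0 + 4.5)/3 = 7.5, ratio 1.25. With two thirds early, r1 = 12.0 and r2 = 3.0, and 2:1 gives 9.0, ratio 1.50.

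**Step 5, scale of the nlcom step.** At f = 1 the period rate ratios are 32.16/6.0 = 5.36 and 4.62/6.0 = 0.77.
- Rate scale, 1:2: (5.36 + 2 × 0.77)/3 = 2.30.
- Log scale, 1:2: exp[(ln 5.36 + 2 ln 0.77)/3] = 1.47.
- Log scale, 2:1: exp[(2 ln 5.36 + ln 0.77)/3] = 2.81.

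Correct weights on the log scale therefore still miss the 12-month ratio.

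**The case against.** One could reply that 2:1 is a slip for later-to-early, since the stated target allows only one answer. That is plausible, but the order in which the rates are named contradicts it, and an analyst would code what is written.

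The stronger objections limit size and reach, and they stand.

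- **Timing is not stated.** A reader might infer that the primary rate ratio is overstated by about two thirds. That needs every Cytosponge-triggered diagnosis to fall within four months. The two-rate model says only that the later rate may differ.
- **The SAP's follow-up factors point lower.** With full front-loading, 9 months of follow-up would give 0.6% × 9/12 = 0.45% against 0.918% + 0.4623% × 9/12 = 1.26%, and the sample size would shrink (factor about 0.80). Section 2.5.4 gives 1.24. In this model 1.24 implies about 78% of these diagnoses by month 9, so at most 78% by month 4 and an excess of at most about 45%. With linear accrual from month 4 to 12, the table rows imply f of about 0.41 to 0.46 and an excess of about 8 to 12%. The derivation file is not shown, so this is indicative only.
- **Other sections pull both ways.** Section 2.3 excludes cases not found by the three systematic methods, most likely those after a positive test, and section 4.1 provides for repeat tests; both could lower the early rate. Against that, section 2.5.1 says patients were invited together, and section 4.1 notes that some late responders could not be offered an appointment.
- **Carrying 2:1 into the regression is an inference.** Section 7.1.1.1 gives no weights for nlcom. The PLR rate ratio is described with study arm as the exposure and names no period effects, although section 7.2 says the primary analysis will be done by period.
- **Not every null is affected.** If the offer changes nothing in either period, any weights give a ratio of 1. The 1.25 and 1.50 above belong to a pure bring-forward scenario.

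**Conclusion.** The weighting rule in section 7.1.1 is wrong as written: 4 and 8 months require 1:2. The direction is certain. The 12-month intervention rate, and any rate ratio built from it, is overstated whenever the early rate exceeds the later one.

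The size is not fixed by the SAP. At its planning values with 27% uptake the excess runs from 0% (one third of Cytosponge-triggered diagnoses early) to at most 67% (all early). It is therefore not supported to state two thirds as the result, or to apply one figure to the CLR, PLR and combined rate ratios alike. Nor does the error create an effect when both period rates equal control; it does so when diagnoses are only brought forward, which the 12-month null hypothesis allows. The point should be corrected before analysis because it sits in the definition of the primary estimate, and because the unstated nlcom scale can move the result as much as the weights do.

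**What to change.** In section 7.1.1, replace the 2:1 rule with: *weighted by time, 4/12 for the rate within four months and 8/12 for the rate from four to 12 months (1:2)*. The later rate can still be estimated from follow-up to 18 months under the constant-rate assumption; only its weight changes.

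In section 7.1.1.1, state that the nlcom step applies these weights on the rate scale: average the intervention rates by time, then divide by the control 12-month rate. State that log rate ratios are not averaged. Apply the same rule in the PLR and combined analyses wherever the two periods are combined.

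The cost is a line or two of wording and code before data lock. The reported rate ratio may become smaller.
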